5.4.1 Dose Modifications

For certain subjects who may be deemed to be at higher risk of bleeding with study drug (e.g. the elderly, small stature, renal impairment), a lower dose of apixaban (2.5 mg BID) will be used. Subjects who fulfill any two of the following criteria will have their apixaban dose reduced to 2.5 mg BID at the time of randomization only:

- I Age ≥ 80 years
- II Body weight ≤ 60 kg
- III Serum creatinine ≥ 1.5 mg/dL

5.5 Blinding

This study will be conducted in a blinded fashion. To maintain blinding of study treatment, study medications will be prepared in a double-dummy design using placebo matching the active treatments. Subjects, Investigators, members of any of the administrative and adjudicating committees, and the Sponsor's staff conducting the study, will not have access to individual subject treatment assignments. The Randomization Center at BMS will have access to such assignments.

5.5.1 Procedure of Blinding

Treatment will be randomized to either adjusted-dose warfarin, target international normalized ratio (INR) 2.0 to 3.0, or fixed-dose apixaban, 5 or 2.5 mg twice daily. Using a double-dummy design to maintain blinding, all patients will receive both assigned anticoagulant and placebo and will be undergo blood sampling at intervals of 30 days or fewer. INR measurements will be by finger-stick sampling using uniform point-of-care devices.

INR testing frequency will occur at least every month during the treatment period, more frequently during titration and if clinically indicated. Each subject will return to have a blood sample drawn and processed in a POC device. The device will deliver an encrypted result to the Investigator who will telephone or electronically transmit the result along with the subject's identification number, date and time to a central response facility. This facility will process the information in a blinded manner and return either a true INR value (in the case of a subject receiving warfarin) or a

[name]

16

sham INR value (in the case of a subject receiving apixaban), along with a dosage recommendation. The final dosing decision will rest with the Investigator.

5.5.2 Unblinding

Blinding is critical to the integrity of this clinical drug trial. However, in the event of a medical emergency or pregnancy in an individual subject, in which knowledge of the investigational product is critical to the subject's management, the blind for that subject may be broken by the treating physician. Before, breaking the blind of an individual subject's blinded treatment, the Investigator should have determined that the information is necessary, i.e., that it will alter the subject's immediate management. In many cases, particularly when the emergency is clearly not investigational product-related, the problem may be properly managed by assuming that the subject is receiving active product without unblinding.

When knowledge of the subject's randomized treatment assignment would have a meaningful impact on individual management, for example in many cases of clinically significant bleeding or the need for urgent invasive procedures, the subject's treatment assignment should be unblinded. This information should be provided to those who are caring for the subject and as few other people as possible. In these cases, we will minimize bias by assuring that the clinical events committee remains blinded to treatment assignment, even if the investigator has been unblinded. The need to break the blind must first be discussed with the responsible Medical Monitor.

5.5.3 Invasive Procedures and Surgery

Several factors govern the management of anticoagulation in this study with respect to surgery and invasive procedures as well as the management of bleeding that may occur in subjects on study drugs.

These are:

- The risk of thromboembolism in an individual subject (low, intermediate or high)
- The risk of bleeding associated with the procedure or surgery
- Whether the surgery or invasive procedure is elective or emergent in nature
- The desirability of maintaining blinding, if at all possible, without creating risk for the subject
- The different times of onset and offset of anticoagulant effect for warfarin and apixaban (warfarin needs to be discontinued earlier than apixaban to permit its effects to abate, and needs to be started in advance of apixaban to achieve a stable anticoagulant effect)

5.5.3.1 *Elective Procedures*

In general, local standards of care for discontinuation of anticoagulation prior to elective procedures/surgery should be employed. These are summarized below based upon the risk of thromboembolism:

High risk of thromboembolism

- Stop warfarin/warfarin-placebo 4 days before the planned procedure.
- Monitor the INR using the encrypted POC device as necessary.
- Begin full dose UFH or LMWH as the INR falls (approximately 2 days before the planned procedure). The doses employed should conform to the local standard of care. Stop apixaban/apixaban-placebo.
- Once the POC INR has attained a value deemed appropriate for the proposed procedure, this value may be confirmed by locally obtained coagulation studies (e.g. INR, PT, aPTT) conforming to the site's standard of care.
- Maintain on UFH or LMWH in the postoperative period as per the local standard of care (full dose preferred) until INR is therapeutic.
- Restart warfarin/warfarin-placebo (usually the night of the day of surgery) and apixaban/apixaban-placebo postoperatively (when the INR is therapeutic) when it is deemed safe to do so. Stop UFH/LMWH.

[name]

17

5.5.3.2 Emergency Procedures

For urgent or emergent invasive procedures, when waiting 4 - 5 days is not an option, management will in part depend on the randomized treatment assignment (warfarin or apixaban) and unblinding may be necessary. Regardless of treatment, study drugs should be discontinued and standard laboratory coagulation tests (PT/INR, aPTT, platelet count, etc.) performed. The procedure should be carried out in such a way to minimize the risk of bleeding.

Subjects receiving warfarin should be managed according to the local standard of care. The anticoagulant effects of warfarin will be reflected in the PT and INR and, after discontinuation, will take several days (3 - 5) to return to normal. Warfarin can be reversed more quickly by giving oral or intravenous vitamin K (depending on circumstances and the local standard of care) and/or with fresh frozen plasma (FFP). Furthermore, for subjects receiving apixaban, the risk of bleeding with invasive procedures is unknown. At therapeutic doses, the anticoagulant effects of apixaban will not be reflected in standard coagulation tests; there is no reversal agent for apixaban. Vitamin K and protamine sulfate are not expected to affect the anticoagulant effect of apixaban, and may carry some risk.

5.6 Concomitant Treatments

5.6.1 Prohibited and/or Restricted Treatments

The following medications or therapies are prohibited:

- Potent inhibitors of CYP3A4 (e.g., azole antifungals [itraconazole and ketoconazole], macrolide antibiotics [clarithromycin and telithromycin], protease inhibitors [ritonavir, indinavir, nelfinavir, atazanavir, and saquinavir], and nefazadone)
- Aspirin > 165 mg/day
- Other antithrombotic agents (e.g., UFH, LMWH, direct thrombin inhibitors, fondaparinux) [Note: UFH and LMWH may be used as part of a bridging strategy, see Section 5.4.1.3 Bridging Strategy.]
- GP IIb/IIIa inhibitors (e.g., abciximab, eptifibatide, tirofiban)

If treatment with an agent above becomes necessary, study drug should be temporarily interrupted, and restarted as soon as possible following discontinuation of the prohibited medication or therapy.

Restricted agents:

The administration of the following agents in subjects on study drug should be done cautiously given the increased risk of bleeding. In such cases, consideration of interruption of the study drug may be warranted; this decision should be made after a careful assessment of the risks and potential benefits.

- Concomitant (simultaneous) use of both aspirin (≤ 165 mg/day) and a thienopyridine (e.g., clopidogrel, ticlopidine)
- Chronic (> 3 months) daily NSAIDs
- Cytotoxic/myelosuppressive therapy

UNIT 6 : Study Assessments & Procedures

6.1 Procedures by Visit

The study is divided into 3 periods as follows:

-Screening period

Screening period of up to 14 days. Subjects who enter the study on warfarin or a VKA may continue in the screening period longer than 14 days until their INR is < 2.0 and they are eligible to be randomized.

-Treatment Period

Lasting until the earlier of a subject's treatment discontinuation or the attainment of 433 primary efficacy events.

[name]

18

-Follow-up Period

Lasting until the latter of 30 days after treatment discontinuation or the attainment of 433 primary efficacy events.

6.1.1 Screening Period

The Investigator will:

- Obtain written informed consent
- Obtain relevant medical history, including history of fractures
- Perform physical examination
- Obtain vital signs
- Obtain physical measurements including height, weight, and hip and waist circumference
- Obtain 12-lead ECG
- Obtain clinical laboratory tests (including INR, preferably from central lab)
- Obtain urine pregnancy test
- Determine if subject meets inclusion/exclusion criteria
- Assess concomitant medication use (within 30 days prior to screening visit)
- Assess previous warfarin/VKA experience

6.1.2 Treatment Period

6.1.2.1 Day 1

After randomization, the Investigator will:

- Administer study drug
- Assess for AEs
- Assess changes in concomitant medication use
- Assess for outcomes (death, stroke, systemic embolism, myocardial infarction, bleeding)

6.1.2.2 All Monthly Visits and INR Visits

INR monitoring will begin on the 4th day following initiation of drug administration and will be performed twice a week for two weeks, once a week for two weeks (i.e. Day 4, Week 1, Day 10, Week 2, Week 3, Week 4), and monthly thereafter once a stable INR is obtained, unless the subject is no longer taking IP. INR measurements are to be reinstated if a subject recommences IP as above. Each subject will return to have a blood sample drawn and processed using the POC device. The device will deliver an encrypted result to the Investigator who will telephone or electronically transmit the result along with the subject's identification number, date and time, to a central response facility. This facility will process the information in a blinded manner and return either a true INR (in the case of a subject receiving warfarin) or a sham INR value (in the case of a subject receiving apixaban), along with a dosage recommendation. The final dosing decision will rest with the Investigator. The POC device may be used prior to randomization to determine if the INR value is < 2 .

At the INR visits the Investigator will:

- Perform POC testing for INR
- Obtain laboratory tests for assessment of LFT and CK (at Months 1 and 2 visits only)
- Obtain urine pregnancy test (at all monthly visits)
- Assess for outcomes (death, stroke, systemic embolism, myocardial infarction, bleeding)
- Assess changes in concomitant medication use (at Month 1 visit only)
- Assess for AEs
- Collect Study Medication
- Assess Study Medication use

[name]

19

- Dispense Study Medication

6.1.2.3 Final Treatment Visit

The Investigator will:

- Obtain 12 Lead ECG (within two months prior to FTV)
- Obtain vital signs
- Obtain clinical laboratory tests including Hematology panel, Chem 21 panel, and urinalysis (within two months prior to FTV)
- Obtain urine pregnancy test
- Assess for fractures (within two months prior to FTV)
- Assess for AEs
- Assess for outcomes (death, stroke, systemic embolism, myocardial infarction, bleeding)
- Assess changes in concomitant medication use
- Collect Study Medication (blinded apixaban may be redispensed to perform bridging and then collected after the last dose is administered, blinded warfarin should be collected at the FTV).
- Assess for Study Medication use

6.1.2 Follow-up Period

Subjects will be followed-up until the later of either 30 days after the last dose with double-blind study drug or the attainment of 433 primary efficacy events. Subjects who discontinued study drug prior to the EOTP date should have a phone call quarterly and if possible a final visit in-person should be performed anytime within approximately 30 days after the attainment of 433 primary efficacy events (EOTP date) but no sooner than 3 weeks after the last dose of double-blind study drug. Subjects who completed the FTV should have a telephone contact approximately 30 days after FTV.

At all follow-up contacts the Investigator or designee will:

- Assess for SAEs (until 30 days after last dose of double-blind study drug)
- Assess for outcomes (death, stroke, systemic embolism, myocardial infarction, bleeding)

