Follow-up Visits: Follow-up of subjects who discontinued study drug prior to the attainment of 433 primary efficacy events in the study should occur quarterly by a telephone call; the final follow-up visit should be in person, if at all possible, and should be performed within approximately 30 days after the attainment of 433 primary efficacy events in the study. Subjects who completed double-blind treatment with study drug should have a telephone contact approximately 30 days after the last dose of double-blind study drug. SAEs (that occurred within 30 days after the last dose of double-blind study drug) and study outcomes will be documented at all follow-up contacts.

Randomization: Eligible subjects will be randomized in a 1:1 ratio to either apixaban or warfarin titrated to a target INR range 2.0 to 3.0. Subjects who are on warfarin or another Vitamin K antagonist (VKA) prior to randomization will have their VKA discontinued prior to randomization. Each arm will contain 7,843 subjects. The randomization will be stratified by investigative site and prior warfarin/VKA status (experienced, naïve). A subject will be classified as warfarin naïve if they have not previously received warfarin or another VKA or have received \leq 30 consecutive days of treatment with warfarin or another VKA in the past. Otherwise the subject will be classified as warfarin experienced.

Duration of Study: The expected duration of the study, from first subject, first visit through the last follow-up phone contact for the last subject, is approximately 60 months.

Number of Subjects per Group: 15,686 subjects (7,843 subjects for each treatment group).

Study Population: Males and females ≥ 18 years of age with AF and one or more of the following additional risk factors for stroke: (1) age ≥ 75 years, (2) previous stroke, transient ischemic attack (TIA) or systemic embolism (SE), (3) symptomatic congestive heart failure or left ventricular dysfunction with an LVEF $\leq 40\%$, (4) diabetes mellitus, or (5) hypertension requiring pharmacological treatment.

Test Product, Dose and Mode of Administration, Duration of Treatment: Oral apixaban 5 mg or 2.5 mg tablets given BID or matching placebo for the treatment period (average of 2.3 yrs of follow-up from randomization).

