7.2 Collection and Reporting

Adverse events can be spontaneously reported or elicited during open-ended questioning, examination, or evaluation of a subject. (In order to prevent reporting bias, subjects should not be questioned regarding the specific occurrence of one or more Aes.)

If known, the diagnosis of the underlying illness or disorder should be recorded, rather than its individual symptoms. The following information should be captured for all Aes: onset, duration, intensity, seriousness, relationship to investigational product, and action taken. The investigator shall supply the sponsor and Ethics Committee with any additional requested information, notably for reported deaths of subjects.

Completion of supplemental CRFs may be requested for AEs and/or laboratory abnormalities that are reported/identified during the course of the study.

Following the subject's written consent to participate in the study, all SAEs must be collected, including those thought to be associated with clinical study procedures. All SAEs must be collected which occur within 30 days of discontinuation of dosing with double-blind study drug. All SAEs must be followed until resolution. In addition, the Investigator should notify BMS of any SAE which may occur after this time period which they believe to be certainly, probably or possibly related to investigational product.

Serious adverse events, whether related or unrelated to investigational product, must be recorded on the SAE page of the CRF and reported expeditiously to BMS (or designee) to comply with regulatory requirements. An SAE report should be completed for any event where doubt exists regarding its status of seriousness.

If the Investigator believes that an SAE is not related to the investigational product, but is potentially related to the conditions of the study (such as withdrawal of previous therapy, or a complication of a study procedure), the relationship should be specified in the narrative section of the SAE page of the CRF. Moreover, if an ongoing SAE

[name]

23

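### The last scheduled contact can fall before the 30-day SAE window closes, for completers bridged with blinded apixaban and for subjects who stop less than 30 days before the 433rd event

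*Protocol*

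**What the plan says.** The requirement is consistent. Protocol section 7.2 states "All SAEs must be collected which occur within 30 days of discontinuation of dosing with double-blind study drug". Section 6.1.2 Follow-up Period lists among the tasks at every follow-up contact "Assess for SAEs (until 30 days after last dose of double-blind study drug", and the same contacts record death, stroke, systemic embolism, myocardial infarction and bleeding. It also sets the overall length (the events meant are those of the primary efficacy endpoint): "Subjects will be followed-up until the later of either 30 days after the last dose with double-blind study drug or the attainment of 433 primary". Sections 4.1 and 6.1 give the same rule.

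The contacts that are meant to deliver this are described less consistently:

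- **Completers, section 6.1.2 Follow-up Period:** "Subjects who completed the FTV should have a telephone contact approximately 30 days after FTV".
- **Completers, synopsis (Follow-up Visits):** they "should have a telephone contact approximately 30 days after the last dose of double-blind study drug".
- **Dosing after the FTV, section 6.1.2.3:** "blinded apixaban may be redispensed to perform bridging and then collected after the last dose is administered".
- **Subjects who stopped before the end-of-treatment-period (EOTP) date, section 6.1.2 Follow-up Period:** quarterly calls and, if possible, a final visit in person that "should be performed anytime within approximately 30 days after the attainment of 433 primary efficacy events (EOTP date"). The section then sets a minimum interval for this visit: "but no sooner than 3 weeks after the last dose of double-blind study drug".

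**The concern.** The SAE window runs from the last double-blind dose, but two of the scheduled contacts are not tied to the end of that window.

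For completers, the synopsis counts from the last dose and section 6.1.2 counts from the FTV. If dosing always ended at the FTV, the difference would be only wording. Section 6.1.2.3 expressly provides for blinded apixaban after that visit, so the two instructions can give different call dates for the same subject.

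For subjects who stopped shortly before the EOTP date, the earliest permitted final visit is at 3 weeks, the window is 30 days, and nothing is scheduled after that visit.

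In both groups an SAE or outcome event late in the window could occur after the last planned contact, and the site would learn of it only if someone volunteered it. Sites that follow the synopsis and sites that follow section 6.1.2 would also call on different days.

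**Working it through.** The protocol gives no figure of its own for coverage, so there is none to reproduce. The check is calendar arithmetic, counting days from the last double-blind dose.

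**Inputs**

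- SAE window: 30 days after the last dose (sections 6.1.2 Follow-up Period and 7.2).
- Completers' call: FTV + 30 days (section 6.1.2 Follow-up Period).
- Bridging after the FTV: *b* days. The protocol gives no value; 2 to 14 days is assumed here to show a range.
- Final visit of subjects who stopped before the EOTP date: not before day 21 after the last dose, and from the EOTP date to about 30 days after it (section 6.1.2 Follow-up Period).
- *s*: days from the last dose to the EOTP date.

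**Completers.** The last dose is at FTV + *b*, so the call falls on day 30 − *b* and the last *b* days of the window come after it.

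| *b* (assumed) | Call on day | Days of window after the call |
|---|---|---|
| 0 | 30 | 0 |
| 2 | 28 | 2 (2/30 = 7%) |
| 7 | 23 | 7 (7/30 = 23%) |
| 14 | 16 | 14 (14/30 = 47%) |

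Without bridging the two anchors coincide and there is no gap.

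**Subjects who stopped before the EOTP date.** The earliest permitted visit is on day max(*s*, 21) and the latest on about day *s* + 30. The largest possible gap is max(0, 30 − max(*s*, 21)).

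| *s* | Permitted visit days | Largest gap (days) |
|---|---|---|
| 1 | 21 to 31 | 30 − 21 = 9 |
| 21 | 21 to 51 | 30 − 21 = 9 |
| 25 | 25 to 55 | 30 − 25 = 5 |
| 29 | 29 to 59 | 30 − 29 = 1 |
| 30 | 30 to 60 | 0 |

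The gap is at most 9 of 30 days (30%). It can arise only when *s* is below 30. Even then a later permitted visit date removes it.

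**Subjects who stopped 30 or more days before the EOTP date.** Every permitted final visit is on day 30 or later. If quarters are counted from the last dose (an assumption), the first call comes at about day 91, which is 91 − 30 = 61 days after the window closes. The synopsis and section 4.1 have every follow-up contact document SAEs that occurred within the 30 days, so this call looks back over the whole window. Capture is late, but the window is covered.

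**The case against.** The strongest reply is that the obligation is never in doubt. Section 7.2 requires every SAE within 30 days to be collected, and section 6.1.2 keeps subjects in follow-up to at least that point. The 3-week figure is a floor, and every late stopper has a permitted visit date on or after day 30. Post-FTV apixaban is optional, the call is only approximately timed, and a short bridge would be absorbed by that. The synopsis already carries the last-dose anchor.

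Much of this stands, and it limits the point to small subsets. It does not remove the point. A duty to collect events needs a contact at which to collect them, and a site that follows section 6.1.2 to the letter can finish its scheduled contacts before the window ends. The word approximately does not tell a site which date to count from.

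Three stronger readings are tempting, and the protocol does not support them:

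- A reader might infer that early stoppers' windows are uncovered because no day-30 call is listed. The look-back at each quarterly call covers them. Nor does the protocol give frequencies to show that these subjects mostly stopped for bleeding.
- A reader might infer that late stoppers leave the study at 3 weeks. The length-of-follow-up rule in the same section says otherwise; the fault is a contact that does not match it.
- A reader might take the remark on differing onset and offset of the two drugs as a warning about the end-of-study switch. It stands in section 5.5.3, on invasive procedures and surgery.

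**Conclusion.** The concern holds for two groups. For completers, the synopsis and section 6.1.2 contradict each other on the anchor date, and section 6.1.2.3 makes the contradiction matter when apixaban is redispensed: the call precedes the end of the window by the length of bridging. The 2 to 14 days is an assumption, and its upper end has no basis in the protocol. For subjects who stopped less than 30 days before the EOTP date, up to 9 days of the window can follow the last scheduled contact; 9 is the worst case.

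The consequence is modest. Primary safety is major bleeding during the treatment period (section 8.3.2), which ends at discontinuation or the 433rd event, whichever is earlier, so the days at issue lie outside it. No effect on the primary efficacy result is shown either. What is at stake is complete recording of post-treatment SAEs and outcomes in small subsets whose size the protocol does not give.

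**What to change.** Reconcile the synopsis (Follow-up Visits), section 6.1.2.3 and section 6.1.2 Follow-up Period on these points:

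1. Time the completers' call no earlier than 30 days after the last dose of any double-blind study drug, including redispensed apixaban, and record the date of that dose.
2. For subjects who stopped less than 30 days before the EOTP date, require the last contact at day 30 or later after the last dose, or add a day-30 telephone call when the visit takes place earlier.
3. Leave the quarterly calls for earlier stoppers as they are.

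The cost is a wording amendment, plus a few days' delay or one extra call for a small number of subjects. The change concerns only the timing of data-collection contacts; it leaves bridging and dosing as they are.
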